12.0 Setting

12.1 Describe all facilities/sites where you will be conducting research procedures.

Include a description of the security and privacy of the facilities (e.g. locked facility, limited access, privacy barriers). Facility, department, and type of room are relevant. Do not abbreviate facility names.

NOTE: Examples of acceptable response may be: "A classroom setting in the Department of Psychology equipped with a computer with relevant survey administration software," "The angiogram suite at Buffalo General Medical Center, a fully accredited tertiary care institution within New York State with badge access," or, "Community Center meeting hall."

Response:

The location will be a private conference room at either RPCI, other cancer provider in WNY, or internet-delivered.

12.2 For research conducted outside of UB and its affiliates, describe:

- *Site-specific regulations or customs affecting the research*
- *Local scientific and ethical review structure*

NOTE: This question is referring to UB affiliated research taking place outside UB, i.e. research conducted in the community, school-based research, international research, etc. It is not referring to multi-site research. UB affiliated institutions include Kaleida Health, ECMC, and Roswell Park Cancer Institute.

Response:

While the study occurs outside of UB, there are no site specific regulations or customs and no local review structures.

N/A: This study is not conducted outside of UB or its affiliates.

13.0 Community-Based Participatory Research

13.1 Describe involvement of the community in the design and conduct of the research.

NOTE: Community-Based Participatory Research (CBPR) is a collaborative approach to research that equitably involves all partners in the research process and recognizes the unique strengths that each brings. CBPR begins with a research topic of importance to the community, has the aim of combining knowledge with action and achieving social change to improve health outcomes and eliminate health disparities.

Response:

Not Applicable" This study does not utilize CBPR.

N/A: This study does not utilize CBPR.

13.2 Describe the composition and involvement of a community advisory board.

Response:

Not Applicable: This study does not have a community advisory board.

N/A: This study does not have a community advisory board.

This proposal poses minimal risks. Anxiety and depression will be assessed at baseline, one-, three- and 12-months post-intervention. Scores greater than seven on either scale will be communicated to participants who will be encouraged to contact their health care provider for follow up care. Any participant who exhibits distress will be asked permission by the study team member they are with to refer them for care as appropriate.

14.4 Describe your process to ensure that all persons assisting with the research are adequately informed about the protocol, the research procedures, and their duties and functions.

Response:

Once this study has IRB approval, the PI will provide the protocol to each member of the research team and then meet with each member of the research team individually to tell the PI what their role on the study will be. Participant safety and data safety and monitoring will also be reviewed.

15.0 Other Approvals

15.1 Describe any approvals that will be obtained prior to commencing the research (e.g., school, external site, funding agency, laboratory, radiation safety, or biosafety).

Response:

Roswell Park Comprehensive Cancer Center (RPCCC): Human Subject Research Committees

N/A: This study does not require any other approvals.

16.0 Provisions to Protect the Privacy Interests of Subjects

16.1 Describe how you will protect subjects' privacy interests during the course of this research.

NOTE: Privacy refers to an individual's right to control access to him or herself. Privacy applies to the person. Confidentiality refers to how data collected about individuals for the research will be protected by the researcher from release. Confidentiality applies to the data.

Examples of appropriate responses include: "participant only meets with a study coordinator in a classroom setting where no one can overhear", or "the

participant is reminded that they are free to refuse to answer any questions that they do not feel comfortable answering.”

Response:

To protect participants' privacy interests during the course of this research, study team members will only meet with the participants in a private clinic room or privately via the internet where no one can overhear the conversation. Additionally, participants will routinely be reminded that they are free to refuse to answer any questions that they feel uncomfortable answering at each data collection period.

16.2 *Indicate how the research team is permitted to access any sources of information about the subjects.*

*NOTE: Examples of appropriate responses include: school permission for review of records, consent of the subject, HIPAA waiver. This question **does apply** to records reviews.*

Response:

Each participant who signs an informed consent will be asked permission by the PI or Study Coordinator to verify diagnostic and treatment information in their electronic medical record. For clinic list prescreening, we have completed a Request for Limited Waiver of the Authorization for the Use of Individually Identifiable Health Information for Subject Recruitment Authorization.

17.0 Data Management and Analysis

17.1 *Describe the data analysis plan, including any statistical procedures. This section applies to both quantitative and qualitative analysis.*

Response:

Specific Aim 1. The primary analyses involve the statistical assessment of Insomnia Severity Index (ISI) at 1 month and will be based on an analysis of covariance (ANCOVA) model. In taking this approach, we fit the dependent variable as a linear function of independent variables randomized treatment assignment, patient cancer type, the interaction between treatment assignment and cancer type, and baseline ISI level. Rather than utilizing the null distribution associated with the classic F-test for overall treatment differences within the ANCOVA framework, which is dependent on the validity of distributional assumptions, an exact permutation testing approach will be utilized. The randomization mechanism at work is a crucial component in this study in that it will be used to create the randomization distribution by which statistical significance will be determined. For more on this approach see Gail, Tan, and Piantadosi (1988)(120). Reported p-values will be obtained from the permutation distributions of the test statistics based on 10,000 Monte Carlo simulations. As additional analyses, subject covariates will be included as independent variables.

The interaction of treatment group and subject covariates may also be examined in a secondary fashion in order to identify possible differential effects of treatment. The analysis of secondary outcomes will proceed in a similar fashion. All statistical tests will be two-sided and tested at a 0.05 nominal significance level.

Specific Aim 2. Standard multiple regression will be used to determine predictors of efficacious response to BBTI. Standard diagnostic plots will be used to assess model fit and transformations of variables may be considered in order to meet statistical assumptions.

Specific Aim 3. Evaluation of BBTI implementation focused on (a) characterization of the patient- and provider-level facilitators and barriers; and (b) knowledge/skills transfer among staff nurses using focus groups with each of the implementation facilitator groups. Transcript-based analysis, the most rigorous and accurate type of qualitative analysis, will be performed on focus group data. Audio recordings of each focus group meeting will be professionally transcribed verbatim and this text will provide the data for analysis. Prior to analysis, accuracy of the transcripts will be verified by [name]. The research team (Drs. [name] and [name]) will read all data repeatedly to achieve immersion and obtain a sense of the whole(121). Then data will be read by highlighting exact words that capture key thoughts or concepts. Next, the researchers will record first impressions, thoughts and initial analysis from the data. Labels for codes will emerge as the process continues. Codes may come directly from the text and become the preliminary coding scheme. Codes will be sorted into categories, which will be used to organize and group codes into meaningful clusters. Final codes will be organized into a hierarchical structure, if possible. Findings will be used to plan for dissemination and sustainability of this intervention. The software, Nvivo, will be used to assist in data management. During years 3 and 5, we will engage implementation facilitators and submit an IRB amendment before implementing aim 3.

17.2 If applicable, provide a power analysis.

NOTE: This may not apply to certain types of studies, including chart/records reviews, survey studies, or observational studies. This question is asked to elicit whether the investigator has an adequate sample size to achieve the study objectives and justify a conclusion.

Response:

The estimate of the variability used for sample size calculations was based on previous results, which showed the standard deviation to be approximately 4.8. Calculations show a sample size of 55 per group (110 total) will allow us to detect differences as small as 3 with 90% power. Since the actual analysis to be performed is based on a model, which incorporates baseline ISI and cancer type, which will account for some of the unexplained variability in the dependent variable, these calculations may be viewed as conservative. Based on our

experience, we expect a 30% drop out rate, thus a total of 158 patients will be enrolled into this study.

17.3 Describe any procedures that will be used for quality control of collected data.

Response:

Participants will receive detailed verbal and written instructions from the PI and study coordinator on how to wear the actiwatch, complete the sleep diaries and self-report questionnaires. Also provided will be how to contact the PI and study coordinator with questions. Reminders and prompts will be provided to participants to avoid unintentional missing data.

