1.0 Objectives

1.1 *Describe the purpose, specific aims, or objectives of this research.*

Response:

Specific Aim 1: To determine the efficacy of Brief Behavioral Treatment for Insomnia (BBTI), experimental condition, compared to Healthy Eating Program (HEP), attention control, on insomnia severity in cancer survivors with insomnia.

Specific Aim 2: To determine predictors for efficacy of BBTI.

Specific Aim 3: To evaluate BBTI implementation with a focus on characterization of the patient- and provider-level facilitators and barriers.

1.2 *State the hypotheses to be tested, if applicable.*

NOTE: A hypothesis is a specific, testable prediction about what you expect to happen in your study that corresponds with your above listed objectives.

Response:

Hypothesis 1: Participants receiving BBTI will exhibit significant and durable improvement in insomnia severity index (key variable), sleep quality, mood, and functional status and quality of life measures over HEP.

Hypothesis 2: Selective demographics (older age), disease stage (stage I), treatment-related (surgery only), mood (nondepressed) and positive beliefs about sleep (needing less than 8-hours of sleep) will predict BBTI efficacy.

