Preliminary Studies The multidisciplinary team assembled for the current project has conducted four studies that involved a homogeneous sample of lung cancer survivors and patients receiving chemotherapy for advanced lung cancer(43-46). These studies established that lung cancer survivors (n=76) experienced middle insomnia (i.e., difficulty maintaining sleep) while patients receiving chemotherapy for lung cancer (n=50) had early (i.e., difficulty falling asleep) and middle (difficulty staying asleep) insomnia(43, 46). Additionally, these studies revealed that lung cancer patients with poor sleep scored significantly lower on measures of quality of life than lung cancer patients with good sleep(47). Eighty-five percent of patients with non-small cell lung cancer (NSCLC) in a longitudinal mixed method study had pre-existing insomnia related to anxiety, cancer- and treatment-related symptoms, and poor sleep hygiene practices(45).

The NIH-funded (1R15NR013779) pilot RCT involved lung cancer survivors who were more than 6 weeks post-surgery for stage I or II NSCLC and \geq 1-year since any other cancer treatment. Recruitment occurred during a routine survivorship clinic visit. Participants (n=44) were screened for sleep disorders with the Sleep Disorders Symptom Checklist(48), ApneaLink plus (AHI<15) and Insomnia Severity Index \geq 8. BBTI was manualized and content about the impact of melatonin, cortisol and nicotine on sleep for lung cancer survivors was added and the attention control intervention, Healthy Eating Program (HEP), was developed(13). No significant differences in baseline ISI were noted between groups ($p=0.11$). Posttreatment ISI mean score was $15.07 +/- 4.42$ for the control group and $6.94 +/- 5.27$ for the BBTI group ($p<0.001$; ES=1.61). Quality of life, using the Functional Assessment of Cancer Therapy-Lung (FACT-L), revealed nonsignificant baseline scores ($p=0.52$), but control group mean scores decreased ($74.67 +/- 26.40$) while BBTI group mean scores increased ($90.73 +/- 21.35$) which revealed a significant between group difference ($p<0.046$). Patients receiving BBTI improved FACT-L by 6.6 points and patients receiving the attention control declined by 14.5 points.

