6.0 Inclusion and Exclusion Criteria

6.1 *Describe the criteria that define who will be **included** in your final study sample.*

NOTE: This may be done in bullet point fashion.

Response:

1. Age \geq 18 years of age
2. \geq 1-month from surgery and \geq 1-month from any other treatment (except for hormone treatment or maintenance targeted therapies) for stages I through III: breast, colorectal, and prostate cancers and stages I through IV: lung cancer.
3. Meet published criteria for chronic insomnia: sleep latency $>$ 30 minutes or wake after sleep onset of $>$ 30 mins for \geq 3 nights/week for at least 1-month
4. ApneaLink Screening Apnea Hyponea Index $<$ 15

5. Ability to complete data collection instruments

6.2 *Describe the criteria that define who will be **excluded** from your final study sample.*

NOTE: This may be done in bullet point fashion.

Response:

1. Other pre-existing sleep disorders except insomnia or obstructive sleep apnea who are CPAP-compliant => 4-hours/night use
2. Unstable medical or psychiatric illness, fibromyalgia, history of seizures, current substance abuse
3. Engaged in night or rotating shift work
4. Travel across two or more time zones within 1 month prior to study participation
5. Inability to complete data collection measures independently
6. Individuals with conditions affecting the non-dominant arm (use of wrist actigraph)

6.3 *Indicate specifically whether you will include any of the following special populations in your study using the checkboxes below.*

NOTE: Members of special populations may not be targeted for enrollment in your study unless you indicate this in your inclusion criteria.

Response:

Not applicable: None of the following special populations will be recruited in the current study.

- Adults unable to consent
- Individuals who are not yet adults (infants, children, teenagers)
- Pregnant women
- Prisoners

6.4 *Indicate whether you will include non-English speaking individuals in your study.*

Provide justification if you will exclude non-English speaking individuals.

*In order to meet one of the primary ethical principles of equitable selection of subjects, non-English speaking individuals may **not** be routinely excluded from research as a matter of convenience.*

In cases where the research is of therapeutic intent or is designed to investigate areas that would necessarily require certain populations who may not speak English, the researcher is required to make efforts to recruit

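### The primary ANCOVA includes a treatment-by-cancer-type interaction, but 17.1 does not say how the four type-specific effects form the overall test, and the power called conservative in 17.2 need not hold if they are weighted equally

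*Combined protocol and SAP*

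**What the plan says.** Section 17.1 (Specific Aim 1) fits ISI at 1 month on "randomized treatment assignment, patient cancer type, the interaction between treatment assignment and cancer type, and baseline ISI level". It replaces the reference distribution of the "classic F-test for overall treatment differences within the ANCOVA framework" with a permutation distribution from 10,000 Monte Carlo draws, two-sided at 0.05. Interactions with other covariates are handled differently: "The interaction of treatment group and subject covariates may also be examined in a secondary fashion".

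Section 6.1 admits four cancer types: "stages I through III: breast, colorectal, and prostate cancers and stages I through IV: lung cancer".

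Section 17.2 takes an SD of about 4.8 and states: "Calculations show a sample size of 55 per group (110 total) will allow us to detect differences as small as 3 with 90% power". It then argues that the figure is conservative: "Since the actual analysis to be performed is based on a model, which incorporates baseline ISI and cancer type", and these account for some of the variability. The interaction is not mentioned there. A 30% dropout allowance brings the total to 158.

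No section gives weights over cancer types, a contrast, degrees of freedom, an expected cancer mix, a baseline-to-outcome correlation, or stratification of the randomization by cancer type.

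**The concern.** Once treatment interacts with cancer type, the model holds four treatment effects, and an overall effect exists only after weights are chosen. At least three ordinary choices fit the wording of 17.1:

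- the treatment coefficient with the interaction left out (a Type II test is nearly the same);
- an average of the four effects weighted by the number of patients of each type;
- an equal-weighted (Type III) average of the four.

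Permutation settles the null distribution but not which statistic is permuted. Two analysts could both follow 17.1 and report different primary p-values. The choices also differ in power when the types are of unequal size, because equal weighting gives the smallest and least precise type a quarter of the weight. The argument in 17.2 that covariates can only help is sound for the first two choices. It does not cover the third.

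**Working it through.** **Inputs from the documents.** Difference 3, SD 4.8, 55 per group, 30% dropout (17.2); two-sided 0.05 and the model terms (17.1); four cancer types (6.1); 1:1 allocation, 79 and 79 (5.1).

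**Assumptions.** The cancer mix p_k and the correlation r between baseline and 1-month ISI are not in the documents, so a range is shown. r = 0 is a floor, since 17.2 expects baseline ISI to explain some variance. The true difference is taken as equal in all four types, with balanced arms within each type unless stated.

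**1. The plan's own figure.** A two-sample t-test with difference 3 and SD 4.8 has power 0.901 at 55 per group and 0.896 at 54. So 55 is right. 110/0.7 = 157.1, which gives 158 as an even total, and 158 x 0.7 = 110.6.

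**2. Additive or patient-weighted test.** The noncentrality is lambda = N d^2 / [4 SD^2 (1 - r^2)].

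- r = 0: 110 x 9 / (4 x 23.04) = 10.74, power 0.901.
- r = 0.4: 10.74/0.84 = 12.79, power 0.943.

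The degrees of freedom are 1 and 104 (additive) or 1 and 101 (patient-weighted). The power is the same to three decimals, whatever the mix.

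**3. Equal-weighted test.** The variance of the contrast is multiplied by V = (1/16) x sum(1/p_k), so lambda is divided by V (df 1 and 101). For 50/20/20/10, V = (2 + 5 + 5 + 10)/16 = 1.375, and at r = 0 lambda = 10.74/1.375 = 7.81.

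| Assumed mix (%) | V | Power, r = 0 | r = 0.4 | r = 0.6 | Difference detectable at 90%, r = 0 / 0.4 |
|---|---|---|---|---|---|
| 25/25/25/25 | 1.00 | 90% | 94% | 98% | 3.0 / below 3 |
| 40/20/20/20 | 1.09 | 87% | 92% | 97% | 3.1 / 2.9 |
| 50/20/20/10 | 1.375 | 79% | 86% | 93% | 3.5 / 3.2 |
| 60/15/15/10 | 1.5625 | 74% | 81% | 90% | 3.7 / 3.4 |

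To restore 90%, baseline ISI must explain 1 - 1/V of the variance: about 27% for 50/20/20/10 and 36% for 60/15/15/10.

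**4. Larger true differences (r = 0, last two mixes).** At 4: 96% and 93%. At 5: 99.6% and 99.1%. At the pilot difference, 15.07 - 6.94 = 8.13 (section 3.1; 44 lung cancer survivors): essentially 100%.

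**5. Permutation simulation with unstratified 55/55 allocation** (an assumption; 4,000 trials, 999 permutations each; standard error 0.4 to 0.7 points). Power at r = 0 / r = 0.4:

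| Statistic | 50/20/20/10 | 60/15/15/10 |
|---|---|---|
| Additive | 88.5 / 93.8% | 88.8 / 93.6% |
| Patient-weighted | 88.1 / 93.6% | 88.5 / 93.6% |
| Equal-weighted | 77.3 / 83.5% | 70.6 / 78.5% |

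The shortfall from steps 2 and 3 comes from chance imbalance within cancer types. In null simulations at r = 0.4, the rejection rate was 0.047 to 0.053 for every statistic tried.

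**The case against.** The strongest reply is that the intended test is clear enough. Section 17.1 speaks of overall differences, Hypothesis 1 is directional ("Participants receiving BBTI will exhibit significant and durable improvement in insomnia severity index (key variable", with further measures, over HEP), and 17.2 plans one difference of 3. Nothing in the documents points to equal weighting, and under the two other readings 17.2 is fair. This stands in part: a single overall effect is surely meant, and a joint 4-df test (73% power at r = 0, 81% at 0.4) is the less likely reading. But a single overall effect from a model with an interaction still needs weights, and equal weighting is an ordinary result of a Type III test in such a model.

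Second, the shortfall needs equal weights, an uneven mix and a modest baseline correlation together, and the last two are assumed here. That is correct, and it makes the power consequence conditional. The 110 completers may also be too few for a 1-month endpoint, because 17.2 ties the 30% dropout to no time point. If loss by 1 month were 15% (assumption; 158 x 0.85 = 134), equal-weighted power in the two most uneven mixes would be 87% and 82% at r = 0, and 92% and 88% at r = 0.4.

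Third, the pilot effect was far above 3: "Posttreatment ISI mean score was $15.07 +/- 4.42$ for the control group and $6.94 +/- 5.27$ for the BBTI group". At that size the choice has no effect on power. But the pilot was small and in lung cancer only, and the trial was planned on 3 in a mixed population.

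A reader might infer that the trial is underpowered or its sample size wrong. The documents do not support that: 55, 110 and 158 reproduce, and the equal-weighted loss is zero with equal type sizes. Nor do they support the inference that the test is invalid, since a statistic fixed in advance keeps its level. A reader might also infer that the choices would estimate materially different effects. That is possible if the effect varies by cancer type, but with the common effect assumed here the targets coincide, and the documents give no type-specific effects from which to size a gap.

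**Conclusion.** The point holds as an unspecified primary test statistic with a conditional cost in power, and it should be fixed. That 17.1 names no weights is a matter of text and needs no assumption. The claim in 17.2 is reasonable for an additive or patient-weighted test. Even there, 90% is met at zero baseline correlation only with balance within types; with unstratified allocation it is about 88-89%, and a correlation of 0.4 brings it to 93-94%. For an equal-weighted test at a difference of 3, power runs from no loss to 74% at zero correlation and 81% at 0.4 over the mixes shown. More uneven mixes would lose more, and a correlation of 0.6 removes the shortfall in the mixes shown. The loss matters near the planned difference of 3, is small at 4 and negligible at 5 or more.

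**What to change.** In 17.1, name the permuted statistic. Preferred: take the primary p-value from the treatment coefficient in a model with treatment, cancer type and baseline ISI, and test treatment by cancer type as secondary, in line with how 17.1 already treats other covariate interactions. Equally acceptable: keep the interaction and permute the average treatment contrast weighted by the observed share of each cancer type.

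In 17.2, tie the statement about conservatism to that named test. If an equal-weighted or joint test is kept instead, restate its power under a stated cancer mix and baseline correlation.

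The cost is one sentence in each subsection, settled before outcome data by arm are seen. No patients or data are added, 55, 110 and 158 stay as they are, and the interaction is still reported.

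### The exact label-permutation rule in section 17.1 does not give exact p-values for the Aim 1 interaction tests, and no other method is named for them

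*Combined protocol and SAP*

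**What the plan says.** Section 17.1, Specific Aim 1, analyses the Insomnia Severity Index (ISI) at 1 month by ANCOVA. The model terms are treatment, cancer type, "the interaction between treatment assignment and cancer type, and baseline ISI level".

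Permutation is introduced as a replacement for the null distribution of "the classic F-test for overall treatment differences within the ANCOVA framework". The plan says that "an exact permutation testing approach will be utilized", and of the randomization mechanism that "it will be used to create the randomization distribution by which statistical significance will be determined". The p-value rule then follows without restriction: "Reported p-values will be obtained from the permutation distributions of the test statistics based on 10,000 Monte Carlo simulations".

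The section next says: "The interaction of treatment group and subject covariates may also be examined in a secondary fashion". It closes with "All statistical tests will be two-sided and tested at a 0.05 nominal significance level".

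For these interactions it gives no null hypothesis, no test statistic, no restricted permutation scheme and no other source of p-values. Aim 2 is assigned ordinary multiple regression and is not tied to permutation.

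**The concern.** Re-drawing treatment labels reproduces the distribution of any statistic exactly when treatment changes nobody's outcome. That hypothesis suits the overall treatment test. The hypothesis of no interaction is different: it allows a common, non-zero effect of BBTI. Under it the labels are not exchangeable, because each outcome carries the effect of the arm the patient was really in.

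The trial expects such an effect. Hypothesis 1 (section 1.2) predicts benefit, and the pilot in section 3.1 reports a post-treatment ISI of 15.07 +/- 4.42 "for the control group and $6.94 +/- 5.27$ for the BBTI group". When labels are permuted, that effect is no longer explained by the model and becomes residual spread. The observed interaction is then compared with a reference distribution that belongs to another hypothesis.

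At stake are the Aim 1 statements on whether BBTI works differently by cancer type or patient characteristics. Two programmers could both follow 17.1, permute different statistics, and reach very different answers from the same data.

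**Working it through.** **The plan's own figures.** Section 17.2 gives SD 4.8, difference 3, 90% power, and 17.1 gives two-sided 0.05. The normal formula is n per arm = 2 × (1.960 + 1.282)² × 4.8² / 3² = 53.8. The t-test version gives 54.8, so 55 per arm (power 0.901). With 30% dropout, 110 / 0.70 = 157.1; per arm 55 / 0.70 = 78.6, so 79 and 158 in total. Both figures reproduce, and the point below does not touch them.

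**Spread under permuted labels.** With 1:1 allocation and main effect d, the outcome SD under permuted labels is √(SD² + d²/4).

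- d = 3 (design difference): √(23.04 + 2.25) = 5.03, a factor of 1.05.
- d = 15.07 − 6.94 = 8.13 (pilot): √(23.04 + 16.52) = 6.29, a factor of 1.31.

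**Unstudentized coefficient.** Its critical value is inflated by that factor, so size is about 2 × [1 − Φ(1.96 × factor)]. This is 0.040 at d = 3 and 0.010 at d = 8.13.

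**Why F also responds to direction.** F rescales by the pooled residual variance, which removes most of the inflation. If a subgroup gains 4 points more, its permuted SD is √(23.04 + 12.13²/4) = 7.73, against 6.29 in the others. If it gains 4 points less, it is √(23.04 + 4.13²/4) = 5.23. Pooling cannot correct a spread that differs between subgroups, so the F reference distribution becomes too wide or too narrow.

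**Simulation, binary moderator.** There were 110 completers, pilot SDs 4.42 and 5.27, and 3,000 trials with 399 permutations each. Assumed: normal errors, a 25% subgroup, a 4-point interaction and a baseline slope of 0.3. The main effect is 8.

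| Rejection rate | Labels, coefficient | Labels, t/F | Classic | Freedman-Lane |
|---|---|---|---|---|
| No interaction (size) | 1.6% | 5.3% | 4.9% | 5.0% |
| Subgroup gains 4 more | 10.1% | 34.6% | 44.5% | 44.2% |
| Subgroup gains 4 less | 36.9% | 52.2% | 45.1% | 44.5% |

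The Monte Carlo standard error is √(0.05 × 0.95 / 3000) = 0.4 points at 5% and about 0.9 points near 45%. Repeat runs, with the main effect at 8 or 8.13, gave:

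- coefficient: size 1.2–1.7%, power 8–10% in the second row;
- classic test: power 42–47% in the second row.

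With the main effect at the design value of 3, power when the subgroup gains 4 more is 27%, 35%, 43% and 43% in the column order above. With a 10% subgroup and a main effect of about 8, label-permuted F has size of about 7–8%, against about 4–5% for the classic test.

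**Simulation, other covariates.** SD 4.8 in both arms, no interaction, main effects 0, 3 and 8.13:

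| Size | d = 0 | d = 3 | d = 8.13 |
|---|---|---|---|
| Continuous, labels, coefficient | 0.051 | 0.040 | 0.0125 |
| Continuous, labels, F | 0.052 | 0.050 | 0.055 |
| Continuous, Freedman-Lane | 0.053 | 0.050 | 0.055 |
| Four equal cancer types, labels, raw sum of squares | 0.044 | 0.037 | 0.005 |
| Four equal cancer types, labels, F | 0.044 | 0.051 | 0.049 |

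For a continuous covariate with an assumed interaction of 2 points per SD, power at d = 3 and d = 8.13 is:

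- label-permuted coefficient: 0.49 and 0.31;
- label-permuted F: 0.53 and 0.57;
- Freedman-Lane: 0.54 and 0.56;
- classic F: 0.55 and 0.58.

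With four cancer types and assumed effects of 6, 6, 6 and 12 points, label-permuted F has 32% power, against 40% for both the classic and Freedman-Lane tests (1,000 trials).

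**The case against.** The strongest reply is that 17.1 never says in so many words that interactions are tested by permuting labels. Permutation enters as a substitute for the overall treatment F-test, and the p-value sentence comes before covariate interactions are raised. That is fair, but the sentence is unqualified and nothing else is offered. If it was meant only for the overall test, the Aim 1 interactions have no stated method, and the same edit is needed.

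Second, the alarming figures come from an unstudentized coefficient that the plan does not name. The plan replaces the null distribution of an F-test, so keeping F is the natural reading, and with F size is close to nominal in most scenarios. This stands. A reader might infer that the interaction tests as planned are strongly conservative. The documents do not support that, because it needs both a raw statistic and an effect near the pilot's 8 points rather than the design's 3.

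Third, the covariate interactions are optional and secondary, and predictors of BBTI efficacy belong to Aim 2. The trial was not sized for interactions: even the classic test has about 44% power in the binary scenario. This also stands and limits the consequence.

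Fourth, choosing Freedman-Lane over label-permuted F is partly preference where both hold size. That is true for balanced or continuous covariates. It is less so for small or unbalanced subgroups, where label-permuted F drifts from the other two.

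**Conclusion.** The concern holds in a limited form. Under the only p-value rule that 17.1 states, Aim 1 interaction p-values are not exact, because the permuted labels represent no effect on anyone and the trial expects an effect.

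With the F statistic the practical error is modest. Size is near 5%, rising to about 7–8% for an assumed 10% subgroup. Power moves by several points: about 10 lower when a 25% subgroup gains more, about 7 higher when it gains less. For a continuous covariate the difference is 1–2 points. With an unstudentized coefficient at the pilot effect the error is large: size 1–2%, and power 8–10% against 42–47% when the subgroup gains more.

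These figures rest on assumed subgroup shares, interaction sizes, baseline slope and normal errors, none of which the documents give. The mechanism and the loss of exactness do not depend on them.

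A reader might also infer that the primary result is in doubt. It is not: the overall treatment test remains exact under the hypothesis of no effect on anyone. The sample size and Aim 2 do not use this procedure for interactions. Nor is there evidence of serious false-positive inflation; the only excess seen was in the small-subgroup case. The change should be made, but the trial's main conclusion does not depend on it.

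**What to change.** In section 17.1, limit exact label permutation to the overall treatment test. For the treatment-by-cancer-type test and any treatment-by-covariate test, state that the null hypothesis is no interaction with the treatment main effect retained, and name the F statistic. Obtain the p-value either by permuting residuals from the model that keeps the main effect (Freedman-Lane) or from the model F-test. Describe these p-values as approximate and the tests as secondary.

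The cost is a few sentences and a few lines of code, with no effect on enrolment, follow-up or the primary analysis. The downside is that the interaction tests lose the nominal label of exactness, which label permutation did not earn for them.
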